3.3.2.3 Task 2.3: Develop risk classification criteria

One of the strengths of the AirCare system is the ability to query the user data on a daily basis to identify patients at high risk for readmission. For example, patients that show low rates of PAP use, increased weight gain, or increased levels of dyspnea, may be at high risk of readmission. The system can generate alerts to health care providers to notify them of this risk so that they can intervene. We will review the symptom data collected during the focus groups to derive preliminary risk classification criteria for non-adherence to PAP therapy for sleep apnea. Candidate targets include low self-report rates of PAP use (such as less than 4 times a week), and persistent oxyhemoglobin desaturations despite PAP therapy (such as persistent desaturations to <90% at night).

3.3.2.4 Task 2.4: Randomized Controlled Trial

The majority of effort during Phase 2 will be devoted to conducting a randomized controlled trial to assess the effectiveness of the AirCareLabs system for reducing 30-day readmission rates in a cohort of heart failure patients with sleep apnea. This study will be conducted at the University of Pennsylvania Health System under the guidance of [name] (sleep medicine), [name] (sleep medicine) and [name] (cardiology), with assistance from [name] and the AirCareLabs team. The proposed study flowchart is shown below.

3.3.2.5 Study Inclusion/Exclusion Criteria:

We have attempted to minimize the study inclusion/exclusion criteria in order to maximize study generalizability. Individuals must meet the following inclusion criteria prior to study enrollment: 1) Acute heart failure exacerbation requiring hospitalization (primary diagnosis) or admitted for another indication, but whose hospital course has become complicated by heart failure exacerbation. 2) Diagnosis of sleep apnea: Established by an apnea-hypopnea index (AHI) ≥ 5 events/hr consisting of predominantly obstructive apneas and hypopneas on full-night portable in-hospital polysomnography. This is the commonly used clinical criteria for sleep apnea in the setting of underlying cardiac disease (American Academy of Sleep Medicine 2005) (Gooneratne et al. 2012). 3) Age ≥ 18 years (see section on “Inclusion of Children”).

Individuals will be excluded from the study for the following reasons: 1) Inadequate sleep apnea treatment with PAP alone: (with up to 2 LPM oxygen) Unable to be adequately treated with PAP to a target AHI<15 events/hr and oxyhemoglobin desaturation nadir >90% and clinical improvement. 2) Unable to perform tests due to inability to communicate verbally, inability to write and read in English; less than a 5th grade reading level; visual, hearing or upper extremity motor deficit (e.g., previous stroke that prevents patient from using PAP treatment).

3.3.2.6 Subject recruitment:

As part of their routine clinical care, patients with active heart failure exacerbation will be evaluated by the sleep in-patient consult service and undergo a portable sleep study. Those with newly diagnosed sleep apnea that elect to start PAP therapy and are adequately treated with PAP therapy will be eligible to participate in the Phase 2 clinical trial. They will undergo an informed consent session using an IRB-approved consent document. Based on our prior experience, we anticipate that approximately 75% will agree to participate. Thus to enroll 240 participants, we must approach 320 heart failure patients with diagnosed sleep apnea. Our preliminary data demonstrated that approximately 80% of admitted heart failure patients have sleep apnea, thus 400 heart failure patients will need to be screened for sleep apnea. The sleep disorders consult service has 10 new consults each week from the cardiology inpatient units for sleep apnea screening, thus approximately 500 new consults per year; we anticipate this volume will be adequate to enroll the required cohort for the Phase 2 study.

We will also recruit subjects from the Presbyterian and Pennsylvania Hospitals, following the same recruitment strategy. We will enroll subjects with a previous OSA diagnosis, who were previously unable to use CPAP. We will also submit a query to the Penn Data store, for de-identified data for the following: age, BMI, gender,

dx of hypertension and CHF, in an effort to expand our recruitment sources. We are also adding an additional recruitment site; Washington University at St. Louis, (WASU), site PI: [name]. This site will follow the same recruitment strategy as Presbyterian and Pennsylvania Hospitals.

3.3.2.7 Study Procedures:

After completing the informed consent process, study participants will complete the following study questionnaires (copies are provided in the Appendix): a) Self-Efficacy Measure for Sleep Apnea (Weaver et al. 2003), b) Self-Care of Heart Failure Index (Riegel et al. 2004), c) RAND Medical Outcomes Study Short Form (SF-36) (Ware et al. 1992), d) Epworth Sleepiness Scale (ESS) (Johns 1993). In addition, the medical chart will be abstracted by the study research coordinator to complete the Cumulative Illness Rating Scale (CIRS), gather demographic data, medications and other relevant covariates (Miller et al. 1992). They will then be randomized in a 1:1 ratio to either the AirCareSystems tablet or standard care as described below:

AirCareSystems Group: Study participants in this arm will receive a tablet computer with a pre-installed AirCare application. The tablet will be locked to prevent other usage. All data from previous users will have been wiped from the tablet. The patient will be instructed in the use of the tablet, and will be encouraged to view the installed educational content created in Phase 1.

At the time of discharge, the study participants will leave the hospital with the PAP unit, the tablet computer and an iHealth oximeter. (In the event the patient is discharged before their PSG, they will use the Embletta at-home sleep device to determine eligibility). At home, they will be asked to complete daily, brief questionnaires about their symptoms. They can also use the tablet to submit queries to request assistance with their sleep apnea care. These queries will be answered during the daytime by the day shift sleep technicians or sleep medical assistants according to the standardized care pathways developed earlier. At night, they will be answered by the sleep technicians staffing the 6 active sleep labs (operating seven days a week on all days except national holidays). They will also use the iHealth oximeter on a nightly basis for the first week, then on an as-needed basis thereafter depending upon their symptoms or requests from care providers. It is anticipated that the average study participant will make 2-5 night-time assistance requests, and 3-7 daytime assistance requests. The Risk Classification criteria developed in Task 2.3 will be applied to identify study participants who are at high risk of non-adherence or readmission.

PAP adherence will also be tracked using the built-in device PAP units. Hospital readmissions, ER visits and other doctor visits will also be recorded.

At the end of the first month of treatment, study participants will be asked to return their tablet and iHealth oximeter. They will also be asked to complete the same battery of study survey instruments they completed at the initiation of the study protocol; this will be repeated at six-month follow-up as well.

Standard Care Group: Study participants in the standard care arm will be asked to complete the same survey instruments shortly prior to discharge. They will leave the hospital with their PAP unit. Out-patient support will be provided by the study participant contacting their Durable Medical Equipment (DME) provider for assistance or their sleep medicine provider through the sleep clinic. At the end of the first month, and again at 6 months, they will be asked to complete the same battery of survey instruments they completed at the initiation of the study protocol. PAP adherence, hospital readmissions, ER visits and other doctor visits will also be tracked

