We have conducted a preliminary analysis of the first 106 consecutive patients from the in-patient program. These 106 patients were on the Hospital of the University of Pennsylvania Cardiology units for congestive heart failure (87.4%, of which 53.3% had New York Heart Association Class 3 and 41.1% had Class 4 heart failure) or other cardiovascular conditions. Of these 106 patients, 81 (78%) were found to have sleep apnea on their diagnostic in-hospital sleep study; this is consistent with findings from other research that suggest a high prevalence of sleep apnea in heart failure patients (Javaheri et al. 1998) (Herrscher et al. 2011). Of these patients, 80% (65/81) had predominantly obstructive sleep apnea and 20% (16/81) had predominantly central sleep apnea. Patients were then started on PAP therapy the next night while in the hospital and continued on PAP therapy at home.

Readmission and Emergency Department visit rates were then monitored as the primary outcome; this occurred in 16.2% of patients within 30 days after discharge. Patients were divided into PAP full users (adherent >4 hours of use a night), partially PAP users (adherent 0 to 4 hours per night) and non-users. The readmission rates are shown in the related Figure. The most striking finding is that while 29-30% of the partial users and non-users were re-admitted within 30 days, none of the PAP full users were re-admitted ($p=0.025$). Also of note, only 34% of the discharged heart failure patients were full users of PAP—the majority of discharged patients were either non-users (30%) or partial-users (36%); this highlights the need to develop interventions to improve PAP

adherence. The manuscript related to these findings is accepted for publication in the Journal of Clinical Sleep Medicine pending revisions (peer-reviewed journal).

While these findings are provocative, it is important to highlight the numerous limitations of the above preliminary data. First, this is a naturalistic quasi-experimental study—the patients were not randomized to PAP or sham-PAP. Second, the study has a small sample size. Third, echocardiographic data and other biomarker data was not available to examine physiologic mechanisms. Fourth, follow-up readmission data and PAP adherence data was only available in 56 out of the 81 patients. Despite these limitations, we believe the above data suggests a possible role for sleep apnea treatment for reducing heart failure readmissions.

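### The 400-to-screen figure counts sleep apnea of any type, but entry requires predominantly obstructive disease; the plan's own data imply at least about 500

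*Combined protocol and SAP*

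**What the plan says.** Section 3.3.2.6 (Subject recruitment) sets out a short recruitment funnel. It expects about 75% of those approached to agree, so 320 must be approached to enroll 240. It then takes from the preliminary data that about 80% of admitted heart failure patients have sleep apnea, and concludes "thus 400 heart failure patients will need to be screened for sleep apnea". It puts the consult service's volume at "10 new consults each week from the cardiology inpatient units for sleep apnea screening, thus approximately 500 new consults per year" and states that "we anticipate this volume will be adequate to enroll the required cohort for the Phase 2 study". The same section adds two hospitals, an outside site and a further group of patients: "We will enroll subjects with a previous OSA diagnosis, who were previously unable to use CPAP". It gives no numbers for any of these.

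Section 3.3.2.5 requires an apnea-hypopnea index of at least 5 events/hr "consisting of predominantly obstructive apneas and hypopneas on full-night portable in-hospital polysomnography".

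Section 3.1.3 describes the preliminary series: "Of these 106 patients, 81 (78%) were found to have sleep apnea on their diagnostic in-hospital sleep study". Of those with sleep apnea, "80% (65/81) had predominantly obstructive sleep apnea and 20% (16/81) had predominantly central sleep apnea". It also reports that 87.4% of the series were inpatients for congestive heart failure; the others had other cardiovascular conditions.

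**The concern.** The prevalence in the funnel and the entry criterion describe different populations. Patients with predominantly central disease count toward the 80% but cannot meet inclusion criterion 2. The 75% cannot absorb them, because it is a rate of agreeing to take part. Section 3.3.2.6 itself speaks only of newly diagnosed sleep apnea, but section 3.3.2.5 says its inclusion criteria must be met before enrollment, so the restriction to obstructive disease applies.

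400 is the only screening requirement in the plan, and the statement that consult volume is adequate follows it directly. If 400 is too low, that statement rests on the wrong comparison, and anyone tracking recruitment against 400 would expect more enrollments than the plan's data support.

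**Working it through.** **Inputs.** From 3.3.2.6: target 240; consent 75%; sleep apnea of any type 80%; 10 consults a week, or about 500 a year. From 3.1.3: 81 of 106 with sleep apnea (printed as 78%); 65 of 81 predominantly obstructive (80%); 87.4% with heart failure. From 3.3.2.10: enrollment in Months 5-17, which is 13 months counted inclusively.

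**The plan's figure reproduces.** 240/0.75 = 320 approached; 320/0.80 = 400 screened. The division is exact.

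**Adding the obstructive-only step.** Number to screen = 320/(any-type rate x obstructive share).

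| Rates used | Qualifying share | Number to screen |
|---|---|---|
| Plan's rounded rates, 0.80 x 0.80 | 64.0% | 320/0.640 = 500 |
| Printed 78% with 65/81 | 62.6% | 320/0.626 = 511 |
| Raw counts, 65/106 | 61.3% | 320/0.6132 = 521.8, so 522 |

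Relative to the stated figure: 500/400 = 1.25 and 521.8/400 = 1.30.

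**In the other direction.** Screening 400 gives 400 x 0.64 x 0.75 = 192, or 400 x (65/106) x 0.75 = 184, against a target of 240.

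**Sampling error in the series.** The Wilson 95% interval for 65/106 is 51.8% to 70.0%. Holding consent at 75%, this gives 320/0.7004 = 457 to 320/0.5181 = 618. The stated 400 lies outside this range.

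**Volume over the enrollment window.** All cardiology consults: 500 x 13/12 = 542, or 10 x 52 x 13/12 = 563. The need is expressed in heart failure patients. If the preliminary heart failure share applied to consults (an assumption), the supply would be 541.7 x 0.874 = 473 to 563.3 x 0.874 = 492. That is above 400 but below 500.

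**Steps still missing.** Section 3.3.2.6 also requires that patients elect to start PAP and are adequately treated. Section 3.3.2.5 excludes inadequate PAP response and limits of language, reading level, or sensory or motor function. The funnel has no rate for any of these. For the newly screened route, 500-522 is therefore a lower bound at the stated rates.

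**The case against.** The strongest reply is that little depends on the 400. It is a planning figure built from approximate inputs; it does not cap screening and is not a sample size or a stopping rule. The section also adds hospitals, an outside site and previously diagnosed patients. This stands, and it keeps the point minor. It does not rescue the number. Extra sites add volume without lowering the number to screen per enrollment, and the previously diagnosed route lowers it by an amount the plan does not give.

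A second reply is that the series is small and mixed. This also stands: 12.6% did not have heart failure, so the rate among heart failure patients alone is not reported. The denominators are also uncertain, since 81/106 is 76.4% and not the printed 78%. That is a reason to write about 500-520 and not a single precise value. But the plan takes its 80% from the same preliminary data, so using the obstructive share from that source is the consistent treatment.

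Two stronger readings are tempting. A reader might compare 542-563 consults with 500-522 needed and infer that supply still exceeds need by a narrow 20-63. The documents do not support that: the comparison sets all cardiology consults against heart failure patients, and the need is itself a lower bound. A reader might instead infer from 473-492 that enrollment will fall short. That is not supported either: the 87.4% share is only assumed to carry over to consults, and the added sources have no numbers.

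**Conclusion.** The point holds as a minor error in a stated figure. It is a mismatch between a planning input and an eligibility criterion; there is no division error. On the plan's own data the number to screen is about 500-522, or 25-30% above 400, before the other eligibility losses. This assumes 75% consent, that all 240 come from new diagnoses (as the 400 also assumes), and that the preliminary shares apply to the trial population.

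Whether the original consult service alone is adequate is not established either way. If the preliminary heart failure share applied to consults, its volume would be below 500, and adequacy would rest at least partly on the added hospitals, the outside site and the previously diagnosed patients. Nothing here shows that recruitment will fail.

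**What to change.** In section 3.3.2.6, add the obstructive-only step and replace the 400. Suggested wording: *At least about 500 (about 500-520) newly screened heart failure patients will be needed to enroll 240 from new diagnoses, before losses from declining PAP, inadequate PAP response and the other exclusions, and fewer if some participants come from the previously diagnosed group.*

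If a percentage is attributed to the preliminary data, use 65/106 (about 61%). The 64% is a product of two rounded rates and was not observed.

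Restate the adequacy sentence against the new number, counting only heart failure consults over Months 5-17, and say how far it relies on the added hospitals, the outside site and the previously diagnosed patients. If the sponsor has rates for PAP acceptance and the other exclusions, add them to the funnel.

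The cost is a few sentences of text, with no change to design, analysis or sample size.

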3.3.2.8 Data Analysis

Descriptive Comparisons Between Intervention Groups at Baseline: Descriptive analyses will be performed in order to characterize the two study groups (AirCare and Standard Care) and to confirm that the randomization resulted in no clinically significant group differences at baseline in demographic, sleep, and other parameters. If the groups differ with regard to baseline variables and these variables are found to have significant associations with outcomes, secondary analysis of covariance will be used to investigate the degree to which estimated relative efficacy depends on these baseline differences.

Hypothesis: The AirCareLabs system will improve PAP adherence post-discharge relative to standard care. Statistical analysis method: PAP adherence will be defined as at least 4 hours of use per night on at least 70% of the study nights (thus, in a typical 30 day month, the study participant will have used it 21 nights for greater than 4 cumulative hours each night); this is consistent with Medicare PAP usage criteria. We will review the PAP adherence downloads, which provide an objective measure of adherence, to determine what percentage of patients in each study arm (AirCare vs. Standard Care) met the adherence criteria (i.e., a patient may be either adherent or non-adherent with PAP). We will utilize a chi-square frequency comparison for this primary analysis.

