3.3.2.9 Sample Size Analysis

The study statistical power will be based on a two-sided Type 1 error rate of 0.05, and a Type 2 error rate of 0.20; these are commonly used criteria for study power calculations.

Hypothesis: We anticipate, based on our preliminary data, that 30% of patients will be fully adherent to PAP therapy (use >4 hours per night for >70% of the month). An improvement in adherence to 50% would represent a clinically meaningful change. Using a power analysis based on the chi-square frequency comparison, we anticipate that a sample size of 93 study participants per group will provide an adequate study power. We will increase this by 30% to factor in study attrition or loss to follow-up, thus a sample size of 120 would be adequate.

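### The trial adds patients previously unable to use CPAP to a newly diagnosed population, but eligibility, randomisation, primary test and sample size do not take account of them.

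*Combined protocol and SAP*

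**What the plan says.** All references are to the combined protocol and SAP.

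- **Eligibility.** Section 3.3.2.6 (Subject recruitment) first states: "Those with newly diagnosed sleep apnea that elect to start PAP therapy and are adequately treated with PAP therapy will be eligible to participate". Its next paragraph, which lists further recruitment sources, states: "We will enroll subjects with a previous OSA diagnosis, who were previously unable to use CPAP". No number, share or cap is given for this group, and inability to use CPAP is not defined. The numbered criteria in 3.3.2.5 refer neither to new diagnosis nor to past CPAP use.
- **Randomisation.** Section 3.3.2.7: "They will then be randomized in a 1:1 ratio to either the AirCareSystems tablet or standard care as described below". No stratification factor is named.
- **Analysis.** Section 3.3.2.8 classes each patient as adherent or not (at least 4 hours a night on at least 70% of nights) and states: "We will utilize a chi-square frequency comparison for this primary analysis". If the arms differ at baseline on variables associated with outcome, a secondary analysis of covariance follows. Prior CPAP failure is not named there.
- **Sample size.** Section 3.3.2.9: "We anticipate, based on our preliminary data, that 30% of patients will be fully adherent to PAP therapy". The comparison rate is a chosen target: "An improvement in adherence to 50% would represent a clinically meaningful change". The result is 93 per group, raised to 120 for attrition. The added group is not mentioned.

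**The concern.** The primary outcome is whether a patient uses PAP enough. A patient recruited because an earlier attempt at CPAP did not work has already done badly on something close to that outcome. Such patients may well have a lower adherence rate than the programme cohort in 3.1.3, which was diagnosed by an in-hospital study and started PAP the next night.

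Three things follow if both groups are enrolled. A likely strong predictor is balanced between arms only by chance, and the primary test does not adjust for it. The pooled difference mixes two populations in an unknown proportion, with no planned result for each. And the 30% has not been reconsidered for the population that will be enrolled. In addition, sites that read different sentences of 3.3.2.6 could admit different patients.

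**Working it through.** **1. The plan's own figure.** Inputs from 3.3.2.9: 30% versus 50%, "two-sided Type 1 error rate of 0.05, and a Type 2 error rate of 0.20". With mean rate m = 0.40:

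n = [1.960 × √(2 × 0.40 × 0.60) + 0.842 × √(0.30 × 0.70 + 0.50 × 0.50)]² / 0.20² = (1.358 + 0.571)² / 0.04 = 93.

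The stated 93 per group is reproduced, with power 0.800. The arithmetic is not at fault.

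**2. Power for a mixed population.** The documents give neither the share f of previously unsuccessful patients nor their adherence, so both are assumed. The remaining patients keep 30% and 50%. The mixed rates are:

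- p1 = (1 − f) × 0.30 + f × c (standard care)
- p2 = (1 − f) × 0.50 + f × t (AirCare)

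where c and t are the assumed rates in the added group. Power = Φ{[(p2 − p1)√n − 1.960 √(2m(1 − m))] / √(p1(1 − p1) + p2(1 − p2))}, with m = (p1 + p2)/2.

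Example, f = 0.25, c = 0.10, t = 0.20, n = 93: p1 = 0.25, p2 = 0.425, m = 0.3375. Power = Φ[(1.688 − 1.311)/0.657] = Φ(0.574) = 0.717.

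| Assumed rates in added group | Share | Mixed rates | n per arm for 80% | Power at 93 | Power at 120 |
|---|---|---|---|---|---|
| 10% vs 20% | 10% | 28.0% vs 47.0% | 101 | 0.77 | 0.86 |
| 10% vs 20% | 25% | 25.0% vs 42.5% | 114 | 0.72 | 0.82 |
| 10% vs 20% | 40% | 22.0% vs 38.0% | 128 | 0.67 | 0.78 |
| 10% vs 30% | 10% | 28.0% vs 48.0% | 92 | 0.81 | 0.90 |
| 10% vs 30% | 25% | 25.0% vs 45.0% | 89 | 0.82 | 0.91 |
| 10% vs 30% | 40% | 22.0% vs 42.0% | 85 | 0.84 | 0.92 |
| 10% vs 10% | 25% | 25.0% vs 40.0% | 152 | 0.59 | 0.70 |

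The column for 93 matches the plan's evaluable number; the column for 120 assumes no loss to follow-up. Power depends on the absolute gain in the added group. A lower control rate alone does not reduce it.

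**3. Chance imbalance.** At a 25% share, the standard deviation of the between-arm difference in share is √(2 × 0.25 × 0.75 / n).

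- n = 120: 0.0559. A gap above 0.10 is 1.79 SD, two-sided probability about 7%.
- n = 93: 0.0635. The gap is 1.57 SD, probability about 12%.

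With the added group at 10% vs 20%, a 10-point gap moves the observed difference by 0.10 × (0.30 − 0.10) = 2 points to 0.10 × (0.50 − 0.20) = 3 points, against a 20-point target.

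**4. Gain from a stratified test.** Take the same case (25% share, 10% vs 20%, n = 93), balanced within strata. The variances become within-stratum averages:

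- null: 0.75 × 0.48 + 0.25 × 0.255 = 0.424
- alternative: 0.75 × 0.46 + 0.25 × 0.25 = 0.4075

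Power = Φ[(1.688 − 1.960 × 0.651)/0.638] = Φ(0.645) ≈ 0.74, against 0.717. The gain is about 2 points.

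**The case against.** The strongest case on the other side has five parts.

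- **Not a formal contradiction.** Section 3.3.2.6 says that newly diagnosed patients are eligible, not that only they are. The added sentence stands among other expansions of recruitment, and 3.3.2.5 aims for minimal criteria and generalisability. This stands: the text is best read as a broadening that was not carried through. It still needs reconciling, because the numbered criteria do not settle the matter.
- **The planning rates may still hold.** A reader might infer that 30% versus 50% no longer describes the population. The documents do not show this. They give no share or adherence rate for the added group, and they do not say that previously diagnosed patients were absent from the programme cohort; that is only inferred from its in-hospital diagnosis. The observed full-user rate was 34%, so 30% is already somewhat below it. Nor do both rates come from that cohort: only the 30% does.
- **The comparison is valid.** A reader might infer bias. Unstratified 1:1 randomisation with a chi-square is unbiased in expectation, and the likely shift from imbalance is small. This stands.
- **A safeguard exists.** The secondary analysis of covariance in 3.3.2.8 could pick up an imbalance. It is conditional and secondary, it does not name this factor, and it fits a yes/no outcome poorly. It answers the point only in part.
- **Stratifying by site as well could create sparse strata.** This stands, and nothing here requires it.

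**Conclusion.** The point holds as a cheap improvement of modest size. The eligibility statements need reconciling, and a plausible strong predictor of the primary outcome is absent from randomisation, the primary analysis and the sample-size reasoning.

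Under the assumed rates and a 25% share, the cost is about 2 power points of precision and a 7% to 12% chance of an imbalance that shifts the difference by 2 to 3 points. The larger loss is interpretive: the pooled result cannot show whether the system helps new users, previously unsuccessful users, or both.

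A reader might conclude that the trial is underpowered. The documents do not support that. At 93 per arm, power is 0.67 to 0.77 over shares of 10% to 40% if the added group gains 10 points, and 0.81 to 0.84 if it gains 20. Which applies is unknown. All these figures rest on assumed shares and rates, and on 30% and 50% holding in the remaining patients.

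**What to change.** 1. Reconcile 3.3.2.5 and 3.3.2.6 so that one statement says who is eligible with respect to new diagnosis and past CPAP use.
2. If both groups are enrolled, define prior PAP failure (yes/no), record it before randomisation, and stratify randomisation by it. Stratifying by site is optional.
3. Make a Cochran-Mantel-Haenszel test over that factor the primary analysis. If randomisation has already begun, at least pre-specify adjustment for it.
4. Report adherence and the between-arm difference by prior-failure status, descriptively.
5. In 3.3.2.9, state the expected share, the assumed rates in each group, and the resulting power as a range.

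The cost is one baseline item, a revised randomisation list and some analysis wording. Stratifying needs no extra patients in itself. The downside is that the restated power may look less favourable than 80%; whether to respond to that with a larger sample is a separate decision.
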